7.8 Protocol Treatment Completion

Subjects who receive 27 total 28-day treatment cycles will be considered as having completed protocol (total of 756 days).

7.9 Off-Therapy / 30 Day Follow-up Visit

Subjects will return to the clinic 30 (+7) days after the last dose of DFMO, and the following evaluations will be conducted:

1. Medical History and Physical examination (including body weight), including documentation of an update of all previous abnormalities, any new abnormalities, and a detailed neurological exam;
2. ECOG Performance status/Lansky Play status (Appendix I);
3. Vital signs, including temperature, pulse rate, blood pressure (sitting);
4. Review and recording of concomitant medications;
5. Monitoring of AEs and review of concurrent illnesses
6. Collect previous cycles drug dosing diaries (if not collected already)

Any subject with a suspected study drug-related toxicity at the follow-up visit must be followed until all current adverse events have resolved to baseline or \leq grade 2. This may require additional clinical assessments and laboratory tests. The follow-up results will be recorded on the appropriate page of the CRF, as well as in the subject's source documentation. Subjects that have started a new anti-cancer treatment since going off DFMO will be censored from any further AE collection at the date of starting the new therapy.

7.10 Survival Follow-up

Subjects will be followed for long term survival by contact with parent or treating institution to confirm survival at the following time points (time from last dose of study drug):

- | | |
|-------------|-------------------------------------|
| - 6 months | -2 years |
| - 1 year | -Yearly after (up to 5 years total) |
| - 18 months | |

Follow up will continue for five (5) years off-therapy or until subject death or subject is lost to follow up (per definition in section 9.0). The follow-up results including follow-up status, remission status, and date of death will be recorded on the appropriate page of the CRF, as well as in the subject's source documentation.

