7.5 Treatment Phase – Cycles 13-27

All Cycles will be 28 days in duration without interruption. The following procedures must be completed:

Cycle 13-27 Day 1

The following procedures may be performed up to +/- 5 days from Day 1:

1. Medical History and Physical examination (including body weight), including documentation of an update of all previous abnormalities, any new abnormalities.
2. Vital signs, including temperature, pulse rate, blood pressure (sitting);
3. Review and recording of concomitant medications;
4. Monitoring and documentation of all AEs and review of concurrent illnesses
5. BSA calculation (from body weight and height);

6. ECOG Performance status/Lansky Play status (Appendix I);
7. Urine for Vanillylmandelic Acid (VMA) & Homovanillic Acid (HVA)
8. Urine for Biological Correlates per section 12.0
9. Urine or serum pregnancy test for female subjects of child bearing potential (onset of menses or ≥ 13 years of age);
10. Collection of previous cycle drug dosing diary and dispensing of new drug dosing diary

Additionally at the start of cycles 14*, 17, 21*, 24, and at off therapy (end of cycle 27)

Windows- The following should be done within +/-5 days of the start of specified cycle. For off-therapy/end of cycle 27 they should be done within 30 days (+7) after stopping study drug:

1. CBC with differential;
2. Serum electrolytes, blood urea nitrogen (BUN), creatinine, bilirubin, LDH, ALT, and AST;
3. C-reactive protein (CRP) and Erythrocyte sedimentation rate (ESR)
4. Optional: Blood for Biological Correlates per section 12.0 (additional consent required)
5. Optional: Blood for Biological Correlates (Circulating Tumor Cells to Houston, TX) per section 12.0 (additional consent required).

* Start of cycles 14 and 21 bloodwork stated above can be done at the same time as the IV is placed for the scans done at the end of cycles 13 and 20 in order to reduce the amount of venipuncture the subject experiences.

End of Cycles 3, 6, 9, 13, 20 and off therapy (cycle 27) – scans may be done more often per institutional standards.

Windows- Scans should be done within +/-14 days of the start of next cycle. Off therapy/end of cycle 27 scans should be done within 30 days (+7) after stopping study drug.

1. MIBG scan (for MIBG avid subjects only). Consider PET scan for non MIBG avid subjects.
2. CT/MRI (use same radiologic method as baseline)

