1. Additional imaging or assessments may be done if clinically indicated. Type of imaging, type of assessment and timing should be recorded as well as reason for imaging and/or assessment.
2. Survival will be monitored on an ongoing basis during the study, then every 6 months from the time the subject is off-treatment for a period of 2 years, then yearly for up to five years off therapy.

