8.2 Documenting Adverse Events

The Investigator should elicit information regarding the occurrence of adverse events through open-ended questioning of the patient, physical examination and review of laboratory results.

All Grade 2 or higher (per CTCAE version 4.0) adverse events, whether serious or not, will be described in the source documents and the adverse event page of the case report form. All new events (Grade 2 or higher), as well as those that worsen in intensity or frequency relative to baseline, which occur after administration of study drug through the period of protocol-specified follow-up, must be captured.

Information to be reported in the description of each adverse event includes:

- A medical diagnosis of the event (if a medical diagnosis cannot be determined, a description of each sign or symptom characterizing the event should be recorded)
- The date of onset of the event
- The date of resolution of the event and whether the event is serious or not
- Action taken; drug treatment required; non-drug treatment required; hospitalization or prolongation of hospitalization required; diagnostic procedure performed; patient discontinued from the study
- Outcome: complete recovery or return to baseline; unknown/lost to follow-up; adverse event persisting; patient died (notify lead site immediately, and complete the Serious Adverse Event page and the Final Visit section of the case report form)

Adverse events, regardless of suspected cause, will be collected for 30 days following the last dose of DFMO and until all current adverse events have resolved to baseline or \leq grade 2.

All adverse events will be reviewed by the safety officer.

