10.4 Event Free Survival

The event free survival (EFS) is defined as the period from the first day of administration of study drug until the first occurrence of relapse, progressive disease, secondary cancer, or death or, if none of these events occurred, until the last contact with the subject.

Progression is defined as the appearance of any new lesions >10mm on CT/MRI, any new lesions on MIBG or new disease present in the bone marrow.

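### For patients who stop DFMO event-free before 2 years, section 7.10 does not specify the relapse dates, secondary cancers or disease evaluations that the EFS endpoint needs

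*Combined protocol and SAP*

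**What the plan says.** Section 10.4 starts the EFS clock at the first dose and runs it "until the first occurrence of relapse, progressive disease, secondary cancer, or death or, if none of these events occurred, until the last contact". Stopping DFMO is neither an event nor a reason to stop counting.

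After treatment, section 7.10 states: "Subjects will be followed for long term survival by contact with parent or treating institution to confirm survival at the following time points". These are 6, 12, 18 and 24 months and then yearly to 5 years, all counted from the last dose. Section 7.7 agrees: "every 6 months from the time the subject is off-treatment for a period of 2 years", then yearly. On what is recorded, section 7.10 says: "The follow-up results including follow-up status, remission status, and date of death will be recorded on the appropriate page of the CRF", and also in the source documents.

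Section 7.5 places scans at the end of cycles 3, 6, 9, 13 and 20 and at off-therapy, the last set within 30 (+7) days of stopping drug. Footnote b of the assessments table gives the same points. Section 7.7 allows further imaging when clinically indicated and asks for its type, timing and reason to be recorded.

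On safety data, section 8.2 says: "Adverse events, regardless of suspected cause, will be collected for 30 days following the last dose of DFMO", and until current events resolve. Section 7.9 ends AE collection when a new anti-cancer treatment starts. Section 8.1.1 counts an event after the follow-up period as an AE only if it is drug-related, and does not treat worsening of the disease under study as an AE.

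**The concern.** The endpoint needs more than the post-therapy contacts are told to collect. For a patient who stops early for toxicity, intercurrent illness, withdrawal of consent to drug, or investigator decision, the plan names no field for the date of relapse or progression, for a secondary cancer, or for the last disease evaluation. Such a patient stays in the primary analysis, because the efficacy population in section 10.2 requires only the first evaluation, generally after 3 cycles.

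Two features add to this. Contacts run from last dose while EFS runs from first dose, so no contact is designed to fall at 2 years. And event-free time extends to the last contact, so a contact that only confirms survival can lengthen EFS without any disease assessment.

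There is no control arm to share the loss. Each missed event counts in favour of DFMO against a fixed 70% rate in Stratum 1 or 10% in Stratum 2. The Kaplan-Meier analysis planned for Stratum 2 also needs event dates.

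**Working it through.** **The plan's own figure.** Inputs from Sample Size and Analysis, Stratum 1 (section 10): null 70%, alternative 80%, one-sided 5%, n = 127. With an exact binomial, the smallest cut-off with error at or below 5% is 98 event-free patients. P(X ≥ 98 | 127, 0.70) = 0.045 and P(X ≥ 98 | 127, 0.80) = 0.820. The stated 80% power is reproduced, and no design figure is in dispute.

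**Who is affected.** Completers are treated for 27 × 28 = 756 days, past 2 years (730 days). The gap therefore concerns only patients who stop earlier.

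**Which EFS components have a named, dated route after the 30-day visit.**

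| Component | Route named in the plan | Date named |
|---|---|---|
| Death | 7.10 | Yes |
| Relapse or progression | 7.10, as remission status | No |
| Secondary cancer | AE only, if drug-related | No separate field |
| Last disease evaluation | None | No |

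**Placing a relapse around day 730.** Contacts fall at stop day + 182.6 × k.

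- Stop at end of cycle 6 (day 168): contacts near days 351, 533, 716 and 898. If the off-therapy set is done at stopping, the scans at the end of cycles 9, 13 and 20 fall away. A loss of remission first reported at day 898 lies between days 716 and 898; 730 − 716 = 14 of those 182 days come before the 2-year mark.
- Stop at end of cycle 9 (9 × 28 = day 252): contacts near days 435, 617 and 800. A loss first reported at day 800 lies between days 617 and 800; 730 − 617 = 113 days come before the mark and 70 after.

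The ambiguity can thus be small or large, depending on the stop date.

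**Upper bound in Stratum 1.** The documents give no early-stopping rate. Assume 10–20% stop event-free and 20–30% of these have an event by 2 years. Then 127 × 0.10 = 12.7 to 127 × 0.20 = 25.4 patients, and 12.7 × 0.20 = 2.5 to 25.4 × 0.30 = 7.6 events. Divided by 127, that is 2 to 6 percentage points if every one were missed.

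**Sensitivity of the tests.** If on average k patients with events are counted event-free, the apparent rate under the null is p0 + k/n.

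| k | Stratum 1: P(X ≥ 98), n = 127, p = 0.70 + k/127 | Stratum 2: P(X ≥ 7), n = 33, p = 0.10 + k/33 |
|---|---|---|
| 0 | 0.045 | 0.042 |
| 1 | 0.067 | 0.130 |
| 2 | 0.095 | 0.273 |
| 3 | 0.132 | – |

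A wider range for Stratum 1 assumes 5–20% stop at 3 to 12 months, a constant hazard giving 70% EFS at 2 years, and 25–100% of later events missed. That gives about 0.3 to 6.8 misclassified patients and a type I error of about 0.050 to 0.36. The top end requires every later event to be missed.

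**The case against.** A reader might infer that the follow-up form records only three items, so that relapse after stopping is not captured at all. The documents do not support this. Section 7.10 introduces its list with the word including, and the form itself is not in the documents, so its full field list cannot be checked. Remission status is among the named items, so a relapse can be known as a status. For the Stratum 1 binomial test, a patient out of remission at a contact before day 730 is a failure with or without an exact date. Deaths are dated.

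A reader might also infer that off-therapy scans appear only in the table's follow-up column, or that 2 to 6 points is the expected bias. Section 7.5 and footnote b both call for off-therapy scans. The 2 to 6 points would require every later event to be missed, including those that remission status and date of death would reveal, so it is a ceiling.

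The synopsis also commits to follow-up until all patients meet the primary and secondary endpoints, and section 7.7 has clinically indicated imaging recorded with its timing.

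All of this stands and narrows the point. It does not supply a dated field for relapse or secondary cancer, a disease evaluation after the off-therapy set, or a contact tied to 2 years from first dose. The synopsis states the aim; section 7.10 does not specify the data that would meet it.

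**Conclusion.** The point holds as a gap in specification. For patients who stop DFMO event-free before 2 years, section 7.10 does not specify the date of relapse or progression, secondary cancer with its date, or the date of the last disease evaluation, all of which EFS as defined in section 10.4 depends on. Events missed, or dated at the later contact that reports them, raise the 2-year EFS.

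The size cannot be estimated from the documents. It depends on the unstated early-stopping rate, on secondary cancers, for which no rate is given, and on how much the remission-status item recovers. The tests are sensitive to small numbers: one misclassified patient on average takes the Stratum 1 error from 0.045 to 0.067 and the Stratum 2 error from 0.042 to 0.130. This should be corrected; sample sizes stay at 127 and 33.

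**What to change.** In section 7.10, have each contact record:

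- the date of any relapse or progression;
- any secondary cancer, with its date;
- the date and result of the last disease evaluation;
- the start date of any new anti-cancer therapy.

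For patients who stopped DFMO early without an event, add one disease-status contact at 24 months from first dose. Collect the results of standard-of-care disease evaluations done up to that date, without mandating extra protocol scans. In section 10.4, censor patients without an event at the last disease evaluation instead of at a contact that only confirmed survival.

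The cost is a few form fields, one added contact, and some extra data retrieval from treating institutions for early stoppers. Some of these patients may then be censored short of 24 months, so the analysis section should say how they enter the 2-year binomial count.

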8.0 Adverse Event Reporting

8.1 Definitions

8.1.1 Adverse Event

An *adverse event* is any untoward medical occurrence in a patient or clinical investigation subject administered a pharmaceutical product and which does not necessarily have to have a causal relationship with this treatment. An adverse event can therefore be any unfavorable and unintended sign (including an abnormal laboratory finding, for example), symptom, or disease temporally associated with the use of a medicinal product, whether or not considered related to the medicinal product.

An untoward medical event which occurs outside the period of follow-up as defined in the protocol will not be considered an adverse event unless related to study drug. Worsening of a medical condition for which the efficacy of the study drug is being evaluated will not be considered an adverse event.

8.1.2 Unexpected Adverse Event

An *unexpected adverse event* is one for which the nature or severity of the event is not consistent with the applicable product information, e.g., the investigator's brochure.

8.1.3 Serious Adverse Event

A *serious adverse event* is any untoward medical occurrence that at any dose:

- Results in death
- Is life-threatening (an event in which the patient was at risk of death at the time of the event; it does not refer to an event which hypothetically might have caused death if it were more severe)
- Requires in-patient hospitalization or prolongation of existing hospitalization
- Results in persistent or significant disability/incapacity
- Is a congenital anomaly or birth defect
- Other important medical events that may not be immediately life-threatening or result in death or hospitalization but may jeopardize the patient or may require intervention to prevent one of the other outcomes listed above. Examples of such events are intensive treatment in an emergency room for allergic bronchospasm; blood dyscrasias or convulsions that do not result in hospitalization; or development of drug dependency or drug abuse.

The term "severe" is often used to describe the intensity (severity) of an event; the event itself may be of relatively minor medical significance (such as a severe headache). This is not the same as "serious", which is based on patient/event outcome or action criteria usually associated with events that pose a threat to a patient's life or functioning.

8.2 Documenting Adverse Events

The Investigator should elicit information regarding the occurrence of adverse events through open-ended questioning of the patient, physical examination and review of laboratory results.

All Grade 2 or higher (per CTCAE version 4.0) adverse events, whether serious or not, will be described in the source documents and the adverse event page of the case report form. All new events (Grade 2 or higher), as well as those that worsen in intensity or frequency relative to baseline, which occur after administration of study drug through the period of protocol-specified follow-up, must be captured.

Information to be reported in the description of each adverse event includes:

- A medical diagnosis of the event (if a medical diagnosis cannot be determined, a description of each sign or symptom characterizing the event should be recorded)
- The date of onset of the event
- The date of resolution of the event and whether the event is serious or not
- Action taken; drug treatment required; non-drug treatment required; hospitalization or prolongation of hospitalization required; diagnostic procedure performed; patient discontinued from the study
- Outcome: complete recovery or return to baseline; unknown/lost to follow-up; adverse event persisting; patient died (notify lead site immediately, and complete the Serious Adverse Event page and the Final Visit section of the case report form)

Adverse events, regardless of suspected cause, will be collected for 30 days following the last dose of DFMO and until all current adverse events have resolved to baseline or \leq grade 2.

All adverse events will be reviewed by the safety officer.

8.3 Expedited Reporting of Adverse Events

All fatal or life-threatening adverse events must be reported to the lead site immediately by telephone, fax, or e-mail within 24 hours of discovery as well as to the appropriate regulatory authorities (local IRB and FDA if required and [REDACTED] as appropriate.). The lead site will then report directly to the safety officer. If full information is not known, additional follow-up by the Investigator will be required.

All other serious adverse events must be reported to the lead site by telephone, fax, or e-mail within 5 days as well as to the appropriate regulatory authorities (local IRB and FDA and [REDACTED] as required and appropriate). Sponsor will aid site in determining FDA reporting requirements for any SAE. All medwatches must be submitted by the sponsor holding the IND and should not be submitted locally by the participating site to the FDA.

The Investigator must report all serious adverse events reported to regulatory authorities in an expedited manner to the local IRB or IEC. All serious adverse events must be followed until resolution or stabilization.

8.4 Grading and Relatedness of Adverse Events

8.4.1 Grading of Severity of an Adverse Event

Each adverse event (Grade 2 or higher) will be graded for severity per the National Cancer Institute Common Terminology Criteria for Adverse Events (CTCAE V 4.0), and these criteria must be used in grading the severity of adverse events. The criteria can be found at: <http://ctep.cancer.gov/reporting/ctc.html>.

Grading of Severity of an Adverse Event Not Listed in Published Criteria:

For those adverse events which are not listed as part of the NCI CTCAE V 4.0, the same grading system should be used, where:

- **Mild** corresponds to an event not resulting in disability or incapacity and which resolves without intervention
- **Moderate** corresponds to an event not resulting in disability or incapacity but which requires intervention
- **Severe** corresponds to an event resulting in temporary disability or incapacity and which requires intervention
- **Life-threatening** corresponds to an event in which the patient was at risk of death at the time of the event
- **Fatal** corresponds to an event that results in the death of the patient

8.5 Relatedness to Study Drug

The Investigator must attempt to determine if an adverse event is in some way related to the use of the study drug and define an attribution category. This relationship should be described as follows:

RELATIONSHIP	ATTRIBUTION	DESCRIPTION
Unrelated to investigational agent/intervention	Unrelated	The AE is clearly NOT related to the intervention. The event is clearly due to causes distinct from the use of the study drug, such as a documented pre-existing condition, the effect of a concomitant medication, or a new condition which, based on the pathophysiology of the condition, and the pharmacology of the study drug, would be unrelated to the use of the study drug.
	Unlikely	The AE is doubtfully related to the intervention. Adverse event does not have temporal relationship to intervention, could readily have been produced by the subject's clinical state, could have been due to environmental or other interventions, does not follow known pattern of response to intervention, does not reappear or worsen with reintroduction of intervention.
Related to investigational agent/intervention	Possible	The AE may be related to the intervention. The event follows a reasonable temporal sequence from administration of the study drug and the event follows a known response pattern to the study drug BUT the event could have been produced by an intercurrent medical condition which, based on the pathophysiology of the condition, and the pharmacology of the study drug, would be unlikely related to the use of the study drug OR the event could be the effect of a concomitant medication.
	Probable	The AE is likely related to the intervention. The event follows a reasonable temporal sequence from administration of the study drug, the event follows a known response pattern to the study drug AND the event cannot have been reasonably explained by an intercurrent medical condition OR the event cannot be the effect of a concomitant medication.
	Definite	The AE is clearly related to the intervention. The event follows a reasonable temporal sequence from administration of the study drug, the event follows a known response pattern to the study drug and based on the known pharmacology of the study drug, the event is clearly related to the effect of the study drug. The adverse event improves upon discontinuation of the study drug and reappears upon repeat exposure.

